Outcome analysis. Suicide attempts as well as service utilization outcomes will be assessed using CareSource's Jail-Medicaid data, which includes Medicaid claims, information on jail booking and release, and other data. As in our past and current studies, this will not be human subjects data because the dataset will not contain personal identifiable information. CareSource will prepare a deidentified dataset that will be made available to authorized research staff through the secure MSU server. Although dates are included in the claims data, all dates relating to the patient, including date of birth, visit dates, dates of labs performed, will be randomly shifted to a fabricated set of dates by CareSource prior to being sent to the research staff. For instance, if a patient's actual visit date was 10/15/2020, CareSource will generate a random date (e.g., 01/30/2001). This will allow us to calculate date and time ranges without using actual patient identifiers.

B. Recruitment and Consent Procedures

Study 1 (Caring Contacts)

Focus Groups:

Provider Focus Groups: Providers will be recruited from the 12 BH agencies via flyers posted in the agencies and on the Internet/social media (e.g., Facebook, LinkedIn). We anticipate recruiting up to 10 providers to provide feedback during each of the focus groups. The initial focus group will be aimed at designing the CC message, while the follow-up focus group will target feedback and problem-solving directed at the use of the CC letters during the study intervention.

Subscriber Focus Groups: Subscribers will be recruited through methods including the use of flyers posted in BH agencies frequented by CareSource subscribers, posting flyers on the Internet/social media, and outreach to participants from a previous study who have given permission to be contacted for future research. Similar to providers, we anticipate recruiting up to 10 subscribers to participate in each of the focus groups (1 initial; up to 2 follow-up).

CC Letters:

After development of the CC letter through stakeholder input in the initial focus groups, CareSource subscribers randomized to the CC group will be mailed CC letters by CareSource. Because this study involves the use of retrospective claims data, individual patients will not be consented for participation. Due to the retrospective nature of the data and the large population, written or verbal consent is not feasible.

Study 2 (Reports, Re-engagement, and Training)

RRT Intervention: Behavioral health providers at the participating agencies will be contacted by Drs. [name] (Butler) and [name] (CareSource) and provided with information about the study. If the provider is willing to participate in the study, they will be emailed a link to review and sign the informed consent in REDCap.

Site Interviews: Primary contacts at the participating agencies will be contacted by [name] (Butler) or her RA and provided with information about the interview. If the provider is willing to participate in the study, they will be emailed a link to review and sign the informed consent in REDCap.

Provider meetings: Providers participating in the RRT Intervention will consent to engaging in monthly meetings as part of the RRT Intervention consent procedure.

C. Potential Risks

Study 1 (Caring Contacts)

Focus Groups:

The main risks associated with focus groups are related to lack of privacy and potential loss of confidentiality. Because focus groups involve multiple people together in an open discussion format, other participants in the group will be aware that the individual participated in the focus group and will be able to hear their input. Focus group participants will be asked to respect the confidentiality of other focus group members by not talking about any content discussed during the meeting, but we have stated in the informed consent that this cannot be guaranteed. No focus group participants will be personally identified in any reports or publications that may result from this study.

CC Letters:

The main risk for subjects randomized to the intervention or control is loss of confidentiality. No patients will be followed prospectively through any direct means of engagement. Caring Contact letters will not contain any information about arrest. However, if the subscriber calls the phone number provided by CareSource and asks why he/she received the letter, the care managers will say that they received word of the subscriber's arrest and wanted to check in with him/her and offer resources and services.

Regardless of the source, all data associated with this project will be stored on servers that adhere to or exceed HIPAA principles and protected using the same protections associated with clinical data. There is only one notable risk in the proposal research study: (1) a breach of confidentiality. Although every effort will be made to minimize this risk, it is possible that a breach of confidentiality (e.g., answers to questions about post-jail release and suicidal thoughts and behaviors) could affect a subject's reputation.

Study 2 : Reports, re-engagement, and training (RRT)

The main risk associated with Study 2 relates to personal difficulties or inconveniences a BH provider may experience during training and delivery of the intervention. Since these activities are within the scope already practiced by the providers, these are considered minor. There is a risk that BH providers will feel coerced to participate since they are agents of CareSource organization, and some of the CareSource leaders are co-investigators.

D. Protection of the Subject

D1. Measures to Minimize Potential Risks

Recruitment and Informed Consent.

Study 1 (Caring Contacts)

All focus group participants will complete an informed consent prior to study involvement. Information provided by focus group members will be identified using a unique code for each participant instead of their names. In addition, to mail checks to the CareSource subscribers who participate in a focus group, we will collect their mailing address for payment purposes. All information will be treated as confidential material and will be available only to authorized research staff. In addition, the University research servers maintain secure environments for storing and processing clinical data that adhere to or exceed HIPAA principles.

CC Letters:

Because this study involves existing patient records within a managed care organization, individual patients will not be consented for participation. Due to the retrospective nature of the data and the large population, written or verbal consent is not feasible. Potential risks due to loss of confidentiality will be minimized by having all information collected and handled by research staff trained to deal appropriately with sensitive clinical issues. All research personnel will receive training in research ethics. All information will be treated as confidential material and will be available only to authorized research staff. CareSource will provide the P50 Center (at MSU) with a limited datafile that will be de-identified by P50 Center (Brown University-based) statisticians. Any results reported with the project will be reported in aggregate.

Study 2 (Reports, Re-engagement, and Training)

Participating providers will complete an informed consent process prior to study involvement; this process will make them aware that they are not required to participate as a condition of employment and that they may use regular work hours to complete training and attend meetings with the researchers.

For Study 1 Focus Group members and Study 2 Providers, any participant may withdraw from the study at any time by notifying the investigators that they would like to withdraw. The informed consent form will state that, unless they specify otherwise, any data that has been collected may be used for the planned analyses.

All research staff will be certified in human subjects education by their respective institutions before having contact with human subjects.

D2. Measures to Ensure Confidentiality

Potential risks due to loss of confidentiality will be minimized by having all information collected and handled by research staff trained to deal appropriately with sensitive clinical issues. All research personnel will receive training in research ethics. All information will be treated as confidential material and will be available only to authorized research staff. All paper-based materials, if applicable, will be kept in locked files. In addition, the University research servers maintain secure environments for storing and processing clinical data that adhere to or exceed HIPAA principles. Therefore, we anticipate the proposed data collection and analysis procedures will pose minimal risk. Only authorized members of the research team will have access to the data. CareSource will provide the P50 Center (at MSU) with a limited datafile that will be de-identified by P50 Center (Brown University-based) statisticians. The Internal Privacy Department at CareSource will review and approve all data de-identification procedures to ensure compliance with the Safe Harbor Method as well as all internal agency protocols prior to the release of any deidentified data for research purposes. Any results reported with the project will be reported in aggregate. Additional data management and security steps are included in the Data Safety and Monitoring Plan.

D3. Data Safety Monitoring Plan

The study investigators will be responsible for implementing and maintaining quality assurance and quality control systems for this study. Written standard operating procedures will be used to guide the research. The PIs (Drs. [name] and [name]) and research staff at their institutions will meet weekly to review study progress, including recruitment, procedures, and unanticipated problems. The protocol will be reviewed and approved by the investigators' IRBs prior to study start. All protocols and procedures will be reviewed with participants (i.e., focus group, providers) prior to study involvement.

Unanticipated problems related to participation in the study will be reported to the PIs or delegated research staff for the duration of the study. The PIs will have the front-line responsibility for identifying potential unanticipated problems experienced by study participants, adjusting the study procedures accordingly, and reporting the experience.

For focus groups/implementation process notes (for which we have identifiable data), the PIs will ensure that information on any adverse effects on provider participants are reported to the IRB/DSMB. If any unanticipated problems are detected, these will be submitted to the respective IRBs and DSMB within 72 hours. The Principal Investigators will be responsible for tracking these reports and relaying them as required to their IRBs.

For Caring Contacts and RRT, CareSource will provide a limited datafile to P50 Center statisticians who will generate a de-identified analytic dataset with aggregated, clinic-level data that will be used by the study team to analyze study findings. Similar to studies conducted in the Mental Health

Research Network, service connection and suicide-related outcomes for these 43,000 individuals are evaluated through claims data. Standard reporting and monitoring “adverse events” as typically defined (i.e., patient death, hospitalization, etc.) in real time is not possible because: (1) claims data lag, and (2) data are aggregated and de-identified. However:

1. All study interventions are either standard of care (reach out to individuals after jail release to see if they need additional mental health or substance use treatment) and we are providing a systematized way to do it (through Caring Contacts or weekly reports to agencies) or are considered suicide prevention best practices (assessment with the C-SSRS and intervention with SPI, the only evidence-based suicide prevention intervention for the target population). Therefore, it seems appropriate to evaluate aggregate outcomes of these system-level efforts to use evidence-based practices.
2. Study interventions take place over 12 months. Because of the lag in claims data (~3 months) and the need to de-identify and integrate datasets to be sent to the PIs, it is not possible for us to have real-time access to the data. However, we will take two steps to provide safety information to the DSMB in a timely way:
 - a. We will have the Data and Safety Monitoring Board (DSMB) review the study prior to the start of the study, and then review extant safety data at 6, 9, and 12 months after the start of the study.
 - b. CareSource estimates that about half of their claims are submitted within 30 days of the service date. Adding time to clean and de-identify the data, run the MHRN algorithm on the data, and prepare the DSMB report, we estimate that about half of claims data will be available for safety review within 60 days of the service date. Therefore, at Month 6, the DSMB will have all the cases from Months 1-3, and half of the cases from Month 4 for review. At Month 9, the DSMB will have all the cases from Months 1-6 and half of the cases from Month 7 for review. At Month 12, the DSMB will have all the cases from Months 1-9, and half the cases from Month 10 for review. Then, the DSMB will have a closeout meeting when all study data are available.

Analyzed participant data will be stripped of personal information by CareSource, and will be identified in the project only by numerical codes. Links between these codes and personal identifiable information (e.g. names) will only exist in the CareSource database (which will not be accessible by research staff). The collected data will be stored on secure servers at Butler and MSU, which are consistently used for data hosting needs. The outcomes of interest will include suicide attempts, engagement with outpatient mental health and substance use services, and returns to jail detention. We will report pre-post intervention changes in the outcomes, both unadjusted, and adjusted for participant characteristics

Most data collected during the study timeframe will be entered into an online data management system (REDCap). Data will be stored on backed up, password protected servers. Within each computer system, only those users authorized to access the data for a given study are able to do so.

Data from focus groups and provider meetings will also be shared with the DSMB. Since no adverse effects are anticipated from these participant groups, any significant negative feedback from these participants will be shared with the DSMB.

Data and Safety Monitoring Board (DSMB)

This project will utilize the central Center DSMB. Our analysis plan will be reviewed and approved formally by the DSMB prior to the start of the study.

E. Potential Benefits

There are no direct benefits from participation in this study, but there are potential benefits.

Participating providers will have the opportunity to be trained in how to address suicide risk assessment

and safety planning, and may be better able to serve the justice-involved population with whom they work.

Individuals passing through jail may benefit from having providers who are more attuned to and better able to meet their needs, which may improve both treatment outcomes and continuity of behavioral health care.

F. Risk-Benefit Ratio

Lack of data sharing is a main reason coordinating health care and jail reentry services has seemed insurmountable. CareSource's Jail-Medicaid data project has bridged this gap to provide an ongoing picture of the justice-involvement of their Medicaid population, making systematic outreach and suicide prevention possible. Further, few previous studies have engaged MCOs in suicide prevention efforts in any capacity. MCOs are an important and innovative suicide prevention partner. Health insurance providers and MCOs have unique access to statewide or even nationwide data on patients at risk for suicide. Actively involving these organizations in suicide prevention can address system fragmentation and result in both improved outcomes and cost-savings. The proposed study will be the first to (1) evaluate CC for individuals released from jail, and (2) evaluate MCO-provided flags for BH re-engagement and suicide prevention services for recently released individuals, a large population that contributes significantly to U.S. suicide rates. The potential benefits outweigh the potential risks. Further, potential risks will be mitigated by ensuring measures to protect participant confidentiality and appropriate data collection and storage.

4) REFERENCES

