RRT Intervention: (participants = BH providers at CareSource Ohio-affiliated BH agencies) From each of the 12 participating BH agencies, 10 providers (for a total of 120 providers overall) will be recruited and consented to participate in the RRT Intervention. These providers potentially treat individuals that are part of the ~6,000 of the 43,000 subscribers passing through jail who have been seen at one of these 12 BH (i.e., mental health and/or substance use) agencies in the 6 months prior to their jail detention.

Site Interviews: Prior to the start of the RRT Intervention, each participating site will be asked to provide information on their site's current procedures and practices including types of services the agency offers, level of services offered, how clients are typically screened for suicide risk, source(s) of funding for the organization, how clients are re-engaged in care, and other questions pertaining to the agency's existing support system(s).

Provider meetings: Approximately 10 BH providers from each of the 12 BH agencies who are participating in the RRT Intervention (N=120).

C2. Study Design

This trial tests effects of two suicide prevention interventions triggered by notification of subscribers' jail release through CareSource's Jail-Medicaid database in a 2x2 factorial design.

Study 1: Caring Contacts

Focus Groups

The first part of this study will involve designing the CC letter message. It is standard in CC interventions to collaborate with individuals with lived experience to tailor specific messages.^{32,83} We will do this in the first 3 months of the project in collaboration with the Center's Methods Core, Consortium Partners, CareSource. This will involve conducting up to 5 separate focus groups with at least 2 groups of CareSource providers and 3 groups of CareSource subscribers (who went through jail in the past year) to ensure that messages are engaging to them following well-established procedures.^{23,47}

Provider Focus Group (up to 10 providers per focus group with up to 2 focus groups [1 initial to design message; 1 additional for feedback/problem-solving]): Providers will be recruited from the 12 BH

Date most recently revised (10/17/23)

Protocol Version: 9

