Following notification of jail release, CareSource will mail CC letters to subscribers randomized to CC (~21,500) monthly for 6 months after jail release. CC involves sending individuals at risk for suicide brief, non-demanding messages of care.^{26,34,45,46} Messages: (1) include a simple expression of care or concern; (2) are non-demanding; and (3) include a reminder of available resources/ways to connect with care. CCs in this study will be addressed from and refer to CareSource's Care Management team via the care management service (CMS) line. This team, who works with individuals to arrange appointments with appropriate providers and other relevant resources (including crisis lines). Individuals who are re-arrested during the 6-month follow-up period will continue to receive letters, but will not be re-randomized.

Caring Contacts fidelity: CC letters sent, the dates they were sent, and any letters returned will be tracked using CareSource's automated mailing system. Since the mailing system is automated, it should involve minimal human error or noncompliance.

Study 2: Reports, re-engagement, and training (RRT)

RRT Intervention will involve 120 BH providers who provide services at 12 of the largest BH agencies in Ohio (10 providers per agency). These agencies serve ~6,000 of the 43,000 CareSource subscribers who passed through jail in the 6 months prior to detention. Providers who consent to participate in the RRT Intervention will receive: (a) notifications of jail release for their clients, (b) instructions for re-engaging these clients in services and training in suicide risk assessment to use at re-engagement; and (c) training in SPI plus notification to use SPI when a client with past suicide attempts is released from jail. Suicide attempts for this proposal will primarily refer to medically-treated (MT) suicide attempts (i.e., presented

to ED/hospital for treatment following a suicide attempt) as these are the only types of attempts we can identify through claims data.

Site Interviews: The primary contacts at each of the participating BH agencies will participate in the site interviews. These will be conducted virtually and will be recorded. Audio/video files recorded during the meeting will be downloaded onto secure servers at Butler and Michigan State University (MSU).

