Training will use Stanley and Brown's well-established methods for videoconference training. SPI and C-SSRS training take about 6 hours total. Prior to the training, individuals will be emailed the SPI manual used in a previous intervention trial (SPIRIT).^{29,46} On the day of the training, information on the rationale for SPI, an overview of SPI, and the steps of SPI, with video clip demonstrations interspersed will be presented. We will provide an additional 30 minutes of training in reaching out to and re-engaging justice-involved individuals in BH care. After completing the online training and study of the written SPI manual, counselors will receive a 2.5 hour live training in SPI fidelity rating via webcam (i.e., it is live, but not in person). The group views and rates fidelity of SPI videos that vary in quality, and then discusses their answers. Drs. Stanley and Brown have found that practicing SPI fidelity assessment by critiquing SPI helped learners understand the SPI model and commit it to memory. C-SSRS training also includes video and live practice. These trainings will be recorded to ensure fidelity and consistency across the trainings. The audio/video files recorded during the meeting will be downloaded onto secure servers at Butler and Michigan State University (MSU).

Weekly reports: During the months BH agencies are assigned to the RRT intervention condition, they will receive weekly reports from CareSource with notifications of jail booking/release dates of any client seen by the agency in the 6 months prior to arrest. Reports will include instructions for how to reengage the client, and a reminder that the C-SSRS can be used for suicide risk assessment. Subscribers with any past (lifetime) suicide attempt documented in available claims data will be flagged for additional outreach and action, including SPI. These reports will be built into an existing, automated CareSource system that

sends jail booking/release data to BH agencies. This system is currently being piloted and refined by CareSource.

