Using the IHI Framework for Going to Full Scale,⁶⁶⁻⁶⁷ this project will focus on sustainability and scalability. We will assess, maximize, and optimize intervention: (1) scalability (per the Intervention Scalability Assessment Tool⁶⁸); (2) sustainability (per the Program Sustainability Assessment Tool⁶⁹⁻⁷⁰) (3) feasibility, acceptability, and appropriateness to providers and systems (per the Acceptability of Intervention Measure,⁷¹ Intervention Appropriateness Measure,⁷¹ and Feasibility of Intervention Measure⁷¹); and (4) actual and recommended implementation strategies (via process mapping and implementation process/case notes).

Statistical power. Assumptions. We conducted a simulation study, allowing for variability in release dates, numbers eligible, and introducing a small intra-cluster correlation (ICC = .01). We assumed 43,000 eligible subscribers for Study 1, with 50% randomly assigned to CC. Based on last year's data, we assumed 6,000 eligible subscribers for Study 2. We expect that ~10% of the 6,000 ($n \sim 600$) will have past suicide attempt identifiable through CareSource claims data. We assumed a six-month risk of suicide attempt 0.05, but past 12-month claims data-identified suicide attempt increases this risk (i.e., .034 in absence of past-year suicide attempt, 0.204 with a past-year suicide attempt, odd ratio (OR) = 5), similar to SPIRIT. **Results.** We ran the simulation model 2001 times. Significance was assessed using a two-tailed type-I error level of 5%. Caring Contacts. We will have 85.6% power to detect an effect equivalent to an OR of 0.89. CC has been found to have much stronger effects than this in previous studies²² suggesting that we are adequately powered for CC. RRT. If we assume an intervention effect for Study 2 of 0.87 OR, we will have 88.3% power to detect this effect. For subscribers with a past year suicide attempt within Study 2 (who will be flagged to receive SPI), we will have 96.4% power to detect an OR of 0.63 (the OR detected for SPI in our previous trial, SPIRIT).⁴⁶ Having superadequate power for this test offsets concerns about providers potentially not providing SPI as instructed in this large, real-world study.

D. Material Inducements

Study 1

Provider focus groups: No material inducements will be provided for BH providers who engage in the focus groups. Providers will complete study-related procedures during work time and are typically not able to accept material inducements.

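### The plan describes RRT delivery both by consenting provider and by agency, and does not say whether the OR of 0.87 behind the 88.3% power is an effect in reached clients or an agency-wide average, so that power is not supported as written.

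*Combined protocol and SAP*

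**What the plan says.** **Delivery by provider.** C1 (RRT Intervention) has 10 providers recruited and consented at each of 12 agencies, 120 in all. Their link to the study population is left open: "These providers potentially treat individuals that are part of the ~6,000 of the 43,000 subscribers passing through jail". C2 (Study 2) lists what they get: "Providers who consent to participate in the RRT Intervention will receive: (a) notifications of jail release for their clients", together with re-engagement instructions, risk-assessment training, SPI training and a prompt to use SPI for clients with past attempts.

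**Delivery by agency.** Specific Aims has the 12 agencies brought online over time and receiving notifications and training. C2 (Training behavioral health providers) randomizes agencies to four cohorts and describes training as going to agencies. C2 (Weekly reports) says of the agencies that "they will receive weekly reports from CareSource with notifications of jail booking/release dates of any client seen by the agency" in the 6 months before arrest, with re-engagement instructions and flags built into the report.

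**Analysis.** C4 Data Analysis uses an indicator for inclusion in Study 2 and one for RRT or Control. It has no term for the treating provider.

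**Power.** C4 (Statistical power) says "we assumed 6,000 eligible subscribers for Study 2" and "If we assume an intervention effect for Study 2 of 0.87 OR, we will have 88.3% power to detect this effect". Its one remark on incomplete delivery concerns the SPI test in subscribers with a past-year attempt. C2 (RRT Fidelity) states that outreach attempts cannot be tracked at scale for the 6,000.

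**The concern.** The two accounts define different exposed populations for the same RRT indicator. If delivery is by provider, a client of a non-consenting clinician in an RRT month is coded as RRT but may receive no part of it. If delivery is by agency, that client is in the weekly report, but the clinician who sees the client may not have had the C-SSRS and SPI training. Either way the analysis estimates an average over reached and unreached clients, and the plan does not say what share is reached.

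Two things are at stake. The first is interpretation: with outreach untracked, a null RRT result would be hard to separate from low reach. The second is the power figure. An OR of 0.87 in reached clients and an OR of 0.87 averaged over all 6,000 are different assumptions, and the first gives less power than stated unless reach is complete.

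**Working it through.** **Inputs from C4 (Statistical power).** Six-month risk 0.05 ("We assumed a six-month risk of suicide attempt 0.05"); OR 0.87; power 88.3%; two-sided 5% level; 6,000 subscribers; ICC 0.01. **From C2.** RRT starts at Months 4, 6, 8 and 10, so the cohorts are exposed for 9, 7, 5 and 3 of 12 months: (9 + 7 + 5 + 3)/48 = 50%. With even release flow and equal cohorts this is about 3,000 exposed against 3,000 control. **Assumed.** Reach c, the share of agency clients whom RRT actually reaches. The documents do not give it.

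**Step 1: try to reproduce the 88.3% at full reach.** An OR of 0.87 on a risk of 0.05 gives odds 0.05263 × 0.87 = 0.04579, a risk of 0.04378.

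- Difference: 0.05 − 0.04378 = 0.00622.
- SE = √[(0.05 × 0.95 + 0.04378 × 0.95622)/3,000] = 0.00546.
- z = 0.00622/0.00546 = 1.14. Power = Φ(1.14 − 1.96) = Φ(−0.82) ≈ 21%.

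The stated figure is not reproduced, and variants do not recover it:

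- One-sided: 31%.
- 3,000 exposed against 40,000 others: 32%.
- All 6,000 exposed against 37,000: 54%.
- 43,000 split 1:1: 86%.
- Stepped-wedge simulation, 1,000 runs, 12 agencies, month and Study 2 terms, ICC 0.01 on the latent scale: 21% with model-based and 24% with cluster-robust standard errors. It omitted the baseline-attempt covariate, the Caring Contacts term and the incarceration offset.

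On the two-proportion formula, 88.3% at OR 0.87 needs about 45,900 subscribers. With 6,000, it corresponds to an OR of about 0.66.

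**Step 2: effect of reach if 0.87 holds only in reached clients and the rest get no benefit.** Average RRT risk = 0.05 − c × 0.00622, converted to an OR. Taking 88.3% at full reach as given, the implied signal is 1.96 + 1.19 = 3.15 standard errors at ln 0.87 = −0.139. Power = Φ(3.15 × ln OR/ln 0.87 − 1.96). The last column repeats the Step 1 formula with the diluted risk.

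| Assumed reach | Average risk | Average OR | Power, taking 88.3% as given | Two-proportion power |
|---|---|---|---|---|
| 100% | 0.0438 | 0.870 | 88% | 21% |
| 90% | 0.0444 | 0.883 | 80% | 17% |
| 75% | 0.0453 | 0.902 | 64% | 13% |
| 50% | 0.0469 | 0.935 | 33% | 8% |
| 25% | 0.0484 | 0.967 | 11% | 5% |

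**Step 3: if 0.87 is instead the average over all 6,000.** Reach then leaves the power unchanged, but the effect in reached clients must be larger. Their risk would be 0.05 − 0.00622/c, which is an OR of 0.83, 0.74 and 0.49 at 75%, 50% and 25% reach.

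**Step 4: caseload implied by full reach.** 6,000/120 = 50 jailed clients per consenting provider per year.

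**The case against.** The best counter-argument is that 0.87 looks like an agency-wide average. Take the roughly 10% with a past attempt at risk 0.204, apply the SPI OR of 0.63 (risk 0.139), and assume no effect in the other 90% at risk 0.034. Overall risk falls from 0.9 × 0.034 + 0.1 × 0.204 = 0.0510 to 0.0306 + 0.0139 = 0.0445, an OR of 0.867. This stands as a plausible reading, but the protocol does not state it. It also still requires every flagged client to be reached: at 75% and 50% reach of that group, the same sum gives 0.90 and 0.93.

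A reader might infer that clients of non-consenting providers are coded RRT but get nothing. The documents do not establish that. Weekly reports cover any agency client, Human Subjects (Subject Population) speaks of at least 120 providers, and nothing says outreach must come from the clinician who saw the client before detention. About 50 clients per provider per year is roughly one a week, which is not plainly out of reach. Under the agency account the Step 2 figures are therefore a worst case at each level of reach.

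Two further points stand. C4 already analyses all Study 2 subscribers by condition, close to an agency-level intention-to-treat analysis. Aim 2, with outpatient claims as a mediator, would help to interpret a null result. Neither settles who receives RRT or what 0.87 means.

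**Conclusion.** The contradiction over the delivery unit is in the current text and must be reconciled. The RRT power of 88.3% is not supported as written, because the meaning of OR 0.87 is unstated and no allowance for reach is attached to that figure.

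It is tempting to conclude that the 88.3% fails because too few clients are covered. The documents do not support that: coverage is not given, and 0.87 may already be an average. The series 80%, 64%, 33% and 11% rests on three assumptions: that 88.3% is right at full reach, that 0.87 applies to reached clients only, and that unreached clients gain nothing.

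The 21% at full reach is a separate caution about the same figure. It shows no visible margin to absorb incomplete reach. It is not proof of error, because the protocol's simulation settings are not shown and baseline adjustment could move the result somewhat, though it would have to close a gap from about 21% to 88%.

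**What to change.** 1. Reconcile C1 (RRT Intervention) and C2 (Study 2) with Specific Aims, C2 (Training behavioral health providers) and C2 (Weekly reports): do reports and flags cover all agency clients, or only those of consenting providers?
2. In C4, state the RRT estimand as the agency-level intention-to-treat effect in all Study 2 subscribers, by the condition of their agency.
3. In C4 (Statistical power), say whether OR 0.87 is the effect in reached clients or the average over all agency clients, and justify it. Rerun the RRT simulation over a stated range of reach, and report its settings.
4. If CareSource claims identify the treating provider, tabulate from pre-detention claims the share of each agency's jailed clients seen by a consenting provider. Treat any analysis restricted to those clients as exploratory, defined identically in control and RRT months.

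Items 1 to 3 cost wording and one rerun of the simulation, and no extra subscribers. The sponsor should accept that the RRT power may come out less favourable. Item 4 is conditional: the extract listed in C4 names no treating-provider field, D3 describes the analytic dataset as aggregated at clinic level, and consenting providers in later cohorts may not be known before rollout begins.
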